AZIENDA USL DI FERRARA – AZIENDA OSPEDALIERO-UNIVERSITARIA DI FERRARA
DIPARTIMENTO INTERAZIENDALE DI CHIRURGIA
U.O. CHIRURGIA GENERALE DELTA – ARGENTA – U.O. CHIRURGIA 1 – U.O. CHIRURGIA 2

Studio Randomizzato Controllato sulla PREABILITAZIONE – Diagramma di Flusso							
	Preoperatorio			Chirurgia	Postoperatorio		
Settimane	-5	-4	-1	0	4	8	52
Case manager	Adesione Inclusione	Basale HRQoL QoL SF-36 GAD-7 PHQ-9	Preoperatorio HRQoL QoL SF-36 GAD-7 PHQ-9	Chirurgia x	Follow up 30 giorni HRQoL QoL SF-36 GAD-7 PHQ-9	Training 8 settimane HRQoL QoL SF-36 GAD-7 PHQ-9	Follow up 1 anno HRQoL QoL SF-36 GAD-7 PHQ-9
Medico dello sport	x	Consenso Informato VO2max Soglia Anaerobica Exercise-ECG 1RM* 6MWT Sit-to-stand test	Consenso Informato VO2max Soglia Anaerobica Exercise-ECG 1RM* 6MWT Sit-to-stand test	x	VO2max Soglia Anaerobica Exercise-ECG 1RM* 6MWT Sit-to-stand test	VO2max Soglia Anaerobica Exercise-ECG 1RM* 6MWT Sit-to-stand test	x
Nutrizionista/ Dietista		Diario dietetico Altezza, peso Calo ponderale % # Circonferenza polso/addome/avan braccio Plica del tricipite Forza presa mano PG-SGA score	Diario dietetico Altezza, peso Calo ponderale % # Circonferenza polso/addome/avan braccio Plica del tricipite Forza presa mano PG-SGA score	x	Altezza, peso Calo ponderale % Forza presa mano PG-SGA score	Altezza, peso Calo ponderale % Forza presa mano PG-SGA score	x
Anestesista	x	x	Visita preoperatoria	ERAS**		x	x
Chirurgo	Informazione Adesione	x	ERAS**	x	Dati ambulatoriali	x	x
Ricercatore	x	x	x	x	Morbilità-mortalità a 30 giorni	Morbilità-mortalità a 60 giorni	Mortalità a 1 anno

* Diverse misurazioni 1RM effettuate mediante: leg press, abdominal crunch, chest press and lateral pull down. ** Linee Guida Enhanced Recovery After Surgery (ERAS) . # calo ponderale negli ultimi 3--6 mesi

AZIENDA USL DI FERRARA – AZIENDA OSPEDALIERO-UNIVERSITARIA DI FERRARA
DIPARTIMENTO INTERAZIENDALE DI CHIRURGIA
U.O. CHIRURGIA GENERALE DELTA – ARGENTA – U.O. CHIRURGIA 1 – U.O. CHIRURGIA 2

- La fase di Adesione (– 5 settimane): nella nostra realtà viene condotta dal Chirurgo alla prima visita pre-operatoria.
Il Nutrizionista/dietista può impostare il diario dietetico

- Nella fase Basale (– 4 settimane): il Medico dello Sport/Fisiatra somministrano il consenso informato alla fase di preabilitazione ed effettuano contemporaneamente i test ergometrici e la prima seduta di allenamento
Il nutrizionista può effettuare le misurazione antropometriche

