- Decrease of PETCO₂ vs workload.
- VE vs VCO₂: change in linearity

Nutritional supplements

To enhance the anabolic effect of physical training, improve lean body mass and obtain or maintain an optimal nutritional status during the prehabilitation period, sufficient intake of nutrients (especially energy and protein) is required. The schedule for the nutritional intervention can be found in Appendix III.

A registered dietician will assess patients' nutritional status at baseline and at the end of the exercise program, using the Patient Generated Subjective Global Assessment (PG-SGA). Furthermore, a set of anthropometric measurements (including body weight, length, triceps skinfold, hand grip strength and circumferences of wrist, waist and upper arm) is performed to allow assessment of (change in) body weight, (subcutaneous) fat mass, (upper limb) muscle mass and muscle strength, taking into account patients' body frame.

The patient will fill in a three-day food diary (including two week days and one weekend day), which will provide an estimate of habitual macronutrient consumption⁵⁴ as analyzed using a commercially available software program.⁵⁵ Based on estimated habitual protein intake, participants will receive a tailored dietary advice aiming a total protein intake of 1,5 (- max 1,8) gram / kg daily.^{56,57} Also, patients will be recommended to evenly 'spread' their protein intake over 3 meals with a minimum of 25-30 gram of protein/ meal.⁵⁸ To stimulate muscle protein synthesis, participants will also be provided with a protein (0,4 gram/kg/day) supplement immediately after strength training (3 times a week) and daily before sleep.

Patients' energy requirements will be estimated according to the revised Harris and Benedict equation⁵⁹ using stress- and activity factors between 1,3 and 1,5. Recommendations to change energy intake will not only be based on discrepancies between estimated energy intake and energy requirements, but also on (changes in) nutritional status parameters, such as weight loss. This is done because underreporting of true energy intake is commonly seen with self-reported dietary assessment^{60, 61} and can increase up to 50% in overweight people.⁶²

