 - Anthropometry. For a first impression of body composition and function, a minimal set of anthropometric measurements are performed. Body weight, length, triceps skinfold, hand grip strength and circumferences of wrist, waist and upper arm are measured. With these measurements, body frame can be determined, and Body Mass Index ($\text{body weight (kg)} / (\text{length})^2$), and muscle- and fat surface area can be calculated. When compared with reference values, one can assess (change in) body weight, (subcutaneous) fat mass, (upper limb) muscle mass and muscle strength, taking into account patients' body frame (S, M, L).¹¹⁰ Measurements will be carried out according to the Anthropometry Procedures Manual of the National Health And Nutrition Survey.¹¹¹

- Body Mass Index will be calculated with the equation body weight (kg)/ body length (cm)². According to the following classification patients' body weight status will be categorized:

- BMI < 18,5 (18-65 years old), BMI < 20 (> 65 years old), BMI < 21 (COPD) underweight
- BMI 18,5/20 or 21(dependent of age/COPD) -24,9 normal weight
- BMI 25 (18-65 years old), BMI 27 (> 65 years old) -30 overweight
- BMI > 30 obesity or severe overweight

- Percentage of body weight loss in the previous 1 and 6 months will be calculated based on the measurement of current body weight and anamnestic required body weight of 1 month or 6 months ago.

- Food diary & 24-hour recall

In the week before start of the training program and in the last week prior to surgery, a three-day food diary will be filled in by the patient and assessed by a registered dietician, to obtain information about patients' food intake. During hospitalization the period (days) of being sober until commencement of oral intake is recorded. At the 5th day of hospital admission, a registered dietician will perform a 24-h recall, to estimate energy and protein intake of the day before and to determine caloric or protein shortage. The energy requirements of the patient are calculated by the Harris-Benedict formula by Roza.^{112, 113}

o Estimated energy requirements

Energy requirements will be estimated using the revised resting energy expenditure (REE) predictive equation of Harris and Benedict,¹¹³ adjusted for relevant stress and activity factors (1,3-1,5).

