13. APPENDICES

Appendix I

Table 1. Prehabilitation randomized controlled trial scheme

Weeks	Preoperative			Operation	Postoperative		
	-5 Before start	-4 Baseline	-1 Preoperative	0 Surgery	4 30 day follow up	8 8 weeks follow up	52 1 year follow up
Gastroenterologist	Inform patient	-	-	-	-	-	-
Sport physician	-	Informed consent VO2max Anaerobic threshold Exercise-ECG	VO2max Anaerobic threshold Exercise-ECG	-	VO2max Anaerobic threshold Exercise-ECG	-	-
Physiotherapist	-	6MWT Stair climb test Sit-to-stand test 1-RM test Activity questionnaire (derived from CHAMPS)	6MWT Stair climb test Sit-to-stand test 1-RM test Activity questionnaire	-	6MWT Stair climb test Sit-to-stand test 1-RM test Activity questionnaire	6MWT Stair climb test Sit-to-stand test 1-RM test Activity questionnaire	-
Dietician		Food diary (3 days) Height, weight Weight loss %* Wrist/abdominal/ Upper arm circumference Skinfold measurements Hand grip strength PG-SGA	Food diary (3 days) Height, weight Weight loss %* Wrist/abdominal/ Upper arm circumference Skinfold measurements Hand grip strength PG-SGA	-			-
Psychologist	-	Intake when indicated (details in protocol)	-	-	-	-	-
Anesthesiologist	-	-	Preoperative screening**	ERAS**	-	-	-
Surgeon	-	-	ERAS**	-	-	-	-
Surgical resident	-	-	-	-	Outpatient data	-	-
Researcher/ Case manager	Inclusion patient	Intake Coping with anxiety HRQoL GAD-7 PHQ-9 Fried Frailty Score G8 score	HRQoL GAD-7 PHQ-9 Program evaluation & health costs (brief)	-	Weight and weight loss %* Hand grip strength PG-SGA score 30-day morbidity and mortality HRQoL GAD-7 PHQ-9 Program evaluation Health costs	Weight and weight loss %* Hand grip strength PG-SGA HRQoL GAD7 PHQ-9	Mortality Activity questionnaire Health and life style HRQoL GAD-7 PHQ-9

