Appendix III: Nutrition

¹Height, weight, wrist circumference, abdominal circumference, upper arm circumference, triceps skinfold, hand grip strength. The following can be calculated: BMI, body frame, (upper limb) muscle mass, (subcutaneous) fat mass.

²% weight loss in previous month and previous 6 months

³Before start prehabilitation, week before surgery, 8 weeks post-surgery

⁴On 4th day of hospital admission (if still in hospital)

⁵Recommended Daily Allowance

Appendix IV: Definitions of complications used after bowel surgery**INTRAOPERATIVE COMPLICATIONS¹**

- *Clinically significant hemorrhage*: intraoperative bleeding requiring transfusion of packed red blood cells (PRBC) during surgery or within 24 hours after surgery
- *Bowel injury*: injury of the small or large bowel requiring intraoperative repair or additional resection.
- *Urinary tract injury*: injury of the ureter or bladder requiring intraoperative repair
- *Vascular injury*: injury of any major vessel (e.g. iliac artery or vein) requiring intraoperative repair
- *Cardiac or respiratory complications*: any cardiovascular (e.g. cardiac arrhythmia, myocardial infarction) or respiratory (e.g. pneumothorax) complication occurring during surgery.
- *Aspiration of gastric content*: intraoperative pulmonary aspiration of gastric content
- *Other*: any intraoperative injury to other viscera (e.g. spleen, vagina)

POSTOPERATIVE COMPLICATIONS**MEDICAL****Cardiovascular**

- *Heart failure*: clinical or radiological signs of congestive heart failure and specific treatment initiated.²
- *Acute myocardial infarction*: increase in cardiac biomarker values or characteristic ECG changes or imaging evidence of new loss of viable myocardium or new regional wall motion abnormality.³
- *Cardiac arrhythmia*: ECG diagnosis of new arrhythmia requiring at least a pharmacologic intervention.⁴
- *Cardiac arrest*: cardiopulmonary resuscitation performed.
- *Deep vein thrombosis*: radiological confirmation of deep vein thrombosis or anticoagulation started due to clinical findings.
- *Pulmonary embolism*: radiological evidence of pulmonary embolism.
- *Cerebrovascular accident*: new focal or global neurologic deficit of cerebrovascular cause that persists beyond 24 h or is interrupted by death within 24 h.⁵

Respiratory

- *Pneumonia*: Hospital acquired pneumonia, defined as presence of lung infiltrate at chest x-ray accompanied with signs of infection and initiation of antibiotic treatment. ⁶

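### The Ferrara flow chart lists a forearm circumference with the triceps skinfold at weeks −4 and −1, where the protocol names the upper arm throughout

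*Protocol*

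**What the plan says.** The Ferrara flow chart (Diagramma di Flusso) at the front of the protocol has a row for the nutritionist/dietician. At weeks −4 and −1 that row lists, among other items, "Circonferenza polso/addome/avan braccio Plica del tricipite". *Polso* is the wrist and *addome* the abdomen. *Avan braccio* is *avambraccio*, the forearm, with the word misspelt or broken. The upper arm would be *braccio*. The chart does not list an upper-arm circumference at any visit.

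The protocol proper names a different third site:

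- Section 5.1 (nutritional supplements): "triceps skinfold, hand grip strength and circumferences of wrist, waist and upper arm".
- Section 8.3 (anthropometry): "Body weight, length, triceps skinfold, hand grip strength and circumferences of wrist, waist and upper arm are measured". It adds: "and muscle- and fat surface area can be calculated". The results are compared with reference values to judge, among other things, upper-limb muscle mass.
- Appendix I, Table 1, dietician's row, weeks −4 and −1: "Upper arm circumference".
- Appendix III, footnote 1: "abdominal circumference, upper arm circumference, triceps skinfold, hand grip strength". Upper-limb muscle mass and subcutaneous fat mass are to be derived from this set.

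Section 3 names Ferrara as one of six centres and applies the measurements to both arms. Section 9.7 lists body composition and nutritional status among the secondary outcomes.

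**The concern.** The triceps skinfold is taken on the upper arm. Estimating limb muscle and fat area from a circumference and a skinfold presumes that both come from the same segment. A forearm circumference paired with a triceps skinfold gives an area that belongs to neither segment. It cannot be read against upper-arm reference values, and it is not the quantity that the other five centres would report under the same name.

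A local chart is also the sheet that site staff are likely to work from. The upper-arm value at week −4 has to be taken then, because it cannot be recovered once prehabilitation has begun. What is at stake is the comparability of one derived body-composition measure across centres, and whether individual Ferrara patients are read correctly against norms.

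**Working it through.** The plan states no figure on this point, so there is none to reproduce. The check is first a comparison of texts, then an illustration of size.

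**1. The sites side by side**

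| Place | Third circumference | Skinfold |
|---|---|---|
| Ferrara chart, weeks −4 and −1 | forearm | triceps |
| Section 5.1 | upper arm | triceps |
| Section 8.3 | upper arm | triceps |
| Appendix I, weeks −4 and −1 | upper arm | site not named |
| Appendix III, footnote 1 | upper arm | triceps |

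The four protocol statements agree with each other, and the chart alone differs.

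**2. Could this be an extraction fault?** Reading a PDF by program can split a word, but it does not add the prefix *avan*. The same wording stands in both visit columns. The Ferrara cell follows the Appendix I cell almost item by item (diary, height and weight, weight loss, three circumferences, skinfold, grip strength, PG-SGA), and the third circumference is where the body site changes.

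**3. Illustration of size, on assumed inputs.** The documents give no area formula, no limb sizes and no skinfold values. Assume a circular limb with circumference C and skinfold T, both in cm:

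- muscle area = (C − πT)² / (4π)
- fat area = C² / (4π) − muscle area

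Example: upper arm 31 cm, forearm 85% of that (26.35 cm), skinfold 1.8 cm, so πT = 5.65 cm.

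- Muscle, upper arm: (31 − 5.65)² / 12.57 = 51.1 cm²
- Muscle, forearm: (26.35 − 5.65)² / 12.57 = 34.1 cm², which is 33% lower
- Fat, upper arm: 31² / 12.57 − 51.1 = 25.4 cm²
- Fat, forearm: 26.35² / 12.57 − 34.1 = 21.2 cm², which is 17% lower

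With the upper arm at 28–34 cm, the forearm at 80–95% of it and the skinfold at 1.0–2.5 cm, computed muscle area falls by 11% to 48% and fat area by 5% to 23%. A second assumed grid (upper arm 27–33 cm, forearm 3–6 cm smaller, skinfold 1.0–2.0 cm) gives 19% to 50% for muscle and 10% to 25% for fat. The direction is downward whenever the forearm is thinner than the upper arm. The size depends wholly on the assumptions.

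**4. Reach.** Both schedules place the circumferences only at weeks −4 and −1. Randomisation is stratified by site (Section 8.2) and both arms are measured in the same way, so any error at Ferrara falls on both arms alike. Neither CCI nor the 6MWT uses these measurements, and the sample size in Section 4.4 rests on CCI.

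**The case against.** The strongest reply is that the chart is a loose local summary and the protocol governs. Section 3 points to Appendix I as the overview of measurements, and Appendix I says upper arm. Section 8.3 requires the measurements to follow a named anthropometry manual. The chart gives no measuring instructions, and its own notes say only that the nutritionist may take the anthropometry at baseline. The chart departs from the protocol elsewhere as well: its weight-loss window is 3–6 months, against 1 and 6 months in Section 8.3; it omits the stair climb test; and it lists VO₂max at week 8. The word may simply be a translation slip, with the upper arm measured in practice.

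Much of this stands. It means that harm is not shown, only possible. It does not remove the contradiction, because a site schedule is there to be followed and this one names a site that the protocol never requests.

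A second reply also has force. No named endpoint is arm muscle area. Section 8.3 says only that the areas can be calculated, as part of a first impression of body composition. PG-SGA, BMI and weight loss do not use an arm circumference at all.

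Three stronger readings are tempting, and the documents do not support them:

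- *That the areas are wrong for every Ferrara patient.* This needs staff to have followed the chart over the protocol and the areas to have been calculated. The documents show neither.
- *That the pooled comparison loses a stated amount of precision.* This would need Ferrara's share of patients, a within-centre SD and an analysis of these areas that ignores centre. The documents give neither of the first two. The single-time-point tests in Section 9.7 are described for postoperative values, whereas these circumferences are preoperative. No inflation figure is defensible.
- *That the error favours one arm.* It would arise alike in both.

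**Conclusion.** The contradiction is certain; its consequence is conditional. The Ferrara chart says forearm where four consistent protocol statements say upper arm. If the chart was followed and the areas are derived, Ferrara's muscle and fat areas would mix two segments and be comparable neither with upper-arm reference values nor with the other centres. Any figure is illustrative: very roughly 10–50% lower for muscle area, on assumed limb sizes and a circular-limb formula that the documents do not give.

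This is a minor inconsistency between a site chart and the protocol. It is not a design decision and it does not threaten the trial's main conclusions. It is worth correcting because the remedy is specific and nearly free.

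**What to change.** In the Ferrara chart, dietician's row, weeks −4 and −1, replace *avan braccio* with the upper-arm circumference (*braccio*), in line with Sections 5.1 and 8.3 and Appendices I and III. Ask the site which segment has been measured so far. Flag any forearm values in the database and leave them out of the muscle- and fat-area calculation. Values confirmed as upper arm can stay.

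The cost is one word in the chart, a short note to the site dietician and a query to the site. No visit, procedure or patient is added. The downside is that any forearm values already taken are lost for this derived variable, and a missed upper-arm value at week −4 cannot be taken afterwards.

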Sponsor	The sponsor is the party that commissions the organisation or performance of the research, for example a pharmaceutical company, academic hospital, scientific organisation or investigator. A party that provides funding for a study but does not commission it is not regarded as the sponsor, but referred to as a subsidising party.
SUSAR	Suspected Unexpected Serious Adverse Reaction
Wbp	Personal Data Protection Act (in Dutch: Wet Bescherming Persoonsgegevens)
WMO	Medical Research Involving Human Subjects Act (in Dutch: Wet Medisch-wetenschappelijk Onderzoek met Mensen)

SUMMARY

Rationale: Colorectal cancer (CRC) is the second most prevalent type of cancer in the World. The only curative treatment is surgical removal of the tumor. However, postoperative complications occur in up to 50% of patients and are associated with a higher mortality- and return of cancer rate and increased hospital costs. The number and severity of complications is closely related to preoperative functional capacity, nutritional state and smoking behavior. Traditional approaches have targeted the per- and postoperative period for rehabilitation and lifestyle changes. However, recent evidence shows that the preoperative period might be the optimal time frame for intervention.

Objective: This study will determine the effects of multimodal prehabilitation on functional capacity and postoperative complications in patients with colorectal cancer.

Study design: International multicenter, prospective, randomized controlled trial.

Study population: Adult patients undergoing elective surgery for colorectal cancer.

Intervention: Patients will be allocated to an intervention group, receiving 4 weeks prehabilitation (group 1, prehab) or to the control group receiving no prehabilitation (group 2, no- prehab). Both groups obtain 8 weeks rehabilitation postoperatively following ERAS guidelines, which is standard care.

Main study parameters/endpoints: The primary endpoints are functional capacity, measured by the 6-minute walk test (6-MWT) and postoperative complications expressed by the Comprehensive Complication Index (CCI). Secondary outcomes include Patient Reported Outcome Measurements (PROMs) such as health related quality of life (HRQoL) (EORTC QLQ-CR29 and EORTC QLQ-C30, RAND questionnaires) and depression and anxiety scores (GAD-7, PHQ-9 questionnaires), functional capacity (VO₂max, sit to stand test, stair climb test, hand grip strength and activity questionnaire), nutritional status, length of hospital stay, study compliance, patient satisfaction and a cost-effectiveness analysis.

Nature and extent of the burden and risks associated with participation, benefit and group relatedness: Side effects might be cardiac arrhythmias or other exercise related problems during the VO₂ maximal intensity exercise tests. Exercise training is not expected to cause any risk to patients. However, since patients are thoroughly screened, we expect to find more pre-existing cardio-pulmonary conditions, for which patients will be referred to either a pulmonologist or cardiologist. The amount of tests might be perceived as a burden for the patients in both groups, as well as the amount of hospital visits for the prehabilitation group.

1. INTRODUCTION AND RATIONALE

Colorectal cancer (CRC) is the second most prevalent type of cancer in the World with over 800.000 patients diagnosed yearly. The only way to cure CRC is by surgical removal of the tumor. However, postoperative complications occur in up to 50% of patients and are associated with a higher mortality- and return of cancer rate, increased hospital costs and a lower Health Related Quality of Life (HRQoL).^{1,2,3} Even in the absence of complications, major surgery is associated with a 20% to 40% reduction in physiological and functional capacity when measured by energy expenditure, endurance time, workload and heart rate during maximum exercise. This reduction in physiologic reserve is experienced as a higher level of fatigue 4-6 weeks after hospital discharge and a return to preoperative baseline functional capacity of only 40%.⁴ The fact that the mean age of colorectal cancer patients is 70 years old, adds up to the risk of irreversible loss of functional capacity during hospital admission.

Fatigue following surgery is manifested by muscular weakness, increased need for sleep and decreased ability to concentrate. It is correlated with preoperative health status, preoperative fatigue, weight, and grip strength, the degree of surgical trauma and intensity of metabolic response, and with postoperative deterioration. Moreover, after operation many patients may need to undergo further treatment like chemotherapy and radiotherapy. This becomes more physically challenging if functional capacity is already lowered due to surgery. If functional capacity is improved preoperatively, postoperative recovery might be faster and adjuvant chemotherapy might be started earlier. This is important since it will result in an increase in survival as reported by recent research findings of the Dutch cancer registry. In this study, 11 000 CRC stage 3 patients were included (2008-2013). 4899 were not treated with chemotherapy and had a 5 years survival of only 39%. If chemotherapy started >12 weeks postoperatively, 5 years survival increased to 54%. Chemotherapy treatment started <6 weeks after operation 5 years survival was further increased to 76%.

Efforts to improve the recovery process have primarily focused on the intraoperative (e.g., minimally invasive surgery, afferent neural blockade) and post-operative periods (e.g., "fast track" early nutrition and mobilization⁵). The latter protocols have been designed to facilitate the return of functional activities and accelerate convalescence. However, the post-operative period may not be the best time to ask surgical patients to make significant changes in their nutrition and exercise, as patients are tired and concerned about perturbing the healing process as well as being depressed and anxious as they await additional treatments for their underlying condition. The pre-operative period may in fact be a better time to intervene in the factors that contribute to recovery beyond the physical and alleviate some of the emotional distress surrounding the anticipation of surgery and the recovery process.⁶ The process of enhancing functional capacity of the individual to enable him or her to withstand an incoming stressor has been termed *prehabilitation*.^{7,8} Although some have used education to prepare patients for procedures,⁹ little has been developed to systematically enhance functional capacity before surgery.

Factors that are strongly associated with complications after colorectal surgery are poor physical condition, nutritional status, cigarette smoking and mental status, and will be individually explained below.

Functional capacity

It has been shown that poor baseline physical performance capacity increases the risk of complications after major non cardiac surgery and prolongs recovery after abdominal surgery. A review on the role of optimizing functional exercise capacity in the surgical population indicated that this approach can result in fewer postoperative complications, shorten the length of hospital stay, reduce disability, and improve quality of life, compared to controls.¹⁰ Based on the notion that preoperative exercise would have an impact on recovery of functional capacity after colorectal surgery, a randomized controlled trial has been performed by [name] et al. This trial, the first and largest trial on surgical prehabilitation, compared two exercise regimens (intense exercise on a stationary bike vs walking and deep breathing) for several weeks before colorectal surgery. The primary outcome was functional walking capacity measured by the six-minute walk test (6MWT) between 5 to 9 weeks postoperatively. Subgroup analysis identified that patients whose functional exercise capacity improved preoperatively, regardless of exercise technique, recovered well in the postoperative period. However, one-third of patients deteriorated preoperatively despite the exercise regimen, and these patients were also at greater risk for prolonged recovery after surgery. Poor preoperative physical function (fatigue, malnutrition and physical performance) and presence of anxiety and depression were also significant confounding predictors of prolonged recovery. These results suggest that exercise training alone is not sufficient to attenuate the stress response in all patients and that it is important to address also factors that promote the beneficial adaptations to training like nutrition and coping behavior. Therefore a new multimodal prehabilitation program was developed multidisciplinary in the Máxima Medical Center together with [name] for the PREHAB trial.

Nutritional status

The role of nutritional status in surgical recovery cannot be underestimated. Evidence from cardiac rehabilitation suggests that exercise attenuates fatigue by facilitating the incorporation of nutrients in tissues and improves quality of life by reducing the impact of anxiety and depression.¹¹ The nutritional status of patients affected by colorectal cancer is directly influenced by the presence of cancer which impacts on all aspects of intermediary (protein, carbohydrate, lipid, trace element, vitamin) metabolism, and by other factors such as age, adjuvant cancer therapy, stage of the disease and by complaints like nausea and fatigue. The greater sensitivity of protein catabolism to nutritional support, in particular to amino acids, could have important implications for the nutritional management of these patients during the period of catabolic stress, with particular emphasis on substrate utilization and energy requirement.¹²

Because most patients are able to eat normally before elective colorectal surgery, and the absorptive capacity of the bowel is not impaired, many CRC patients have seemingly normal preoperative nutritional status.^{13,14} However, consumption of energy and protein is often low in patients about to undergo colonic surgery and malnutrition or unintended weight loss occurs in up to 36,4% of CRC patients.^{13,15,16,17,18,19} In undernourished patients, especially loss of lean body mass (muscle mass) is associated with adverse outcome. In oncology patients, the presence of low lean body mass may be related to lower tolerance to (neo)adjuvant therapy.^{20,21} Furthermore, malnutrition with unintended weight loss and/or low lean muscle mass in (CRC) surgery patients is associated with more post-operative complications, delayed recovery of bowel function, prolonged length of hospital stay, higher re-admission rates, higher costs, reduced quality of life, and higher incidence of postoperative morbidity and mortality.^{13,22,23}

Emerging is that a normal or high body weight, occurring in most CRC patients, may hide underlying muscle wasting.¹³ Most of CRC patients are 60 years or older, and in this age group anabolic resistance is known to be highly prevalent. Anabolic resistance implies a reduced capability to synthesize muscle protein in reaction to anabolic stimuli (i.e. exercise and protein) and results in muscle wasting. Inflammatory disease, reduced physical activity and inadequate intake of energy, protein and vitamin D enhance the age-related loss of muscle mass, also known as sarcopenia (loss of muscle mass with increased or stable fat mass).^{24,25,26,27}

Sarcopenia and sarcopenic obesity (sarcopenia in combination with high body weight) are associated with reduced muscle strength, functional decline, physical disability, increased risks of fractures and falls, enhanced risk of metabolic disease, increased length of hospital stay and decreased survival in general populations of older adults.^{25,28,29,30}

Preoperative nutritional intervention in malnourished patients with unplanned weight loss, aiming improvement of nutritional status, has been shown an effective strategy for reducing risk of post-surgery complications such as infections and anastomotic leaks.¹³

Preoperative nutritional interventions focusing on improvement of lean body mass in CRC patients with sarcopenia or sarcopenic obesity in order to improve post-surgical outcome, have gained less attention.

Cigarette smoking

Cigarette smoking itself is a well-known risk factor for postoperative complications. Smoking has a transient effect on the tissue microenvironment and a prolonged effect on inflammatory and reparative cell functions leading to delayed healing and complication.³¹ Wound contraction and collagen metabolism are also affected by a smoking-induced alteration in vitamin C turnover and by a change in inflammatory cell response.³² Evidence exists that preoperative smoking interventions reduce postoperative morbidity. Moreover, smoking cessation restores the tissue microenvironment rapidly and the inflammatory cellular functions within 4 weeks. Therefore, smoking cessation a few weeks before surgery is likely to reduce the risk of all complications, as well as the major complication CAL. A period of 4 to 8 weeks smoking cessation prior to surgery has already been shown to significantly reduce postoperative complications.³³

Mental status

Psychological status may also play an important role in surgical recovery. It is well documented that patients awaiting major surgery experience anxiety concerning their upcoming operation, its outcome, and their course of healing and recovery.^{34,35} They may also feel depressed, hold unrealistic expectations (overly optimistic or pessimistic) about their health status, and possess inadequate strategies for coping with pre- and post-operative periods. Any of these factors may influence pain³⁶ and interfere with post-operative functioning.^{37,38}

Multimodal prehabilitation

Although exercise, nutritional interventions, smoke cessation and psychological interventions prior to surgery have separately shown to improve several post-surgical outcome parameters, no studies have been performed investigating a *combined* multimodal intervention approach in preoperative CRC patients. This is a huge gap in our knowledge. It is already known that a strong interaction exists between exercise and nutrition, and their synergistic effects on muscle protein synthesis have been associated with gains in muscle mass, increased muscle strength, improved functional capacity and better functional performance in studies among other older populations.³⁹

When physical activity is performed closely before ingestion of a meal-like amount of dietary protein, the blunted anabolic response in healthy older individuals can largely be overcome.⁴⁰ A protein enriched diet with protein supplementation during resistance training programs has been shown to enhance fat free mass,^{41, 42} improve 1-RM leg press strength (the maximum weight a person can press with his/her leg,⁴¹ and preserve muscle mass even during intentional weight loss intervention.²⁷

Protein is the fundamentally anabolic nutrient.⁴³ Besides protein ingestion immediately post-exercise (30-40 g), a higher overall dietary protein intake, ample protein consumption evenly divided across all meals (25-30 g per meal) and protein ingestion before sleep are associated with a prolonged anabolic effect of physical training. Importantly, studies have demonstrated that with ample amounts of amino acids, an anabolic state can be obtained even in patients with cancer.⁴⁴ Finally, vitamin D is associated with muscle mass and strength.^{45, 46, 47}

Since it has been established that the number and severity of complications is closely related to preoperative functional capacity, nutritional status, smoking behavior and psychological well-being, there is a growing need to target these issues by means of the implementation of a multimodal intervention program. From a physiological point of view and based on limited practical experience, it seems feasible to achieve clinically relevant effects during the frame of 4-5 weeks between diagnosis and operation. However, this will only be achieved if targeted interventions involving exercise, nutrition, smoke cessation and psychological support are implemented.^{48,49,50,51,52}

